#### *Bone marrow or blood cytogenetic analysis*

*Bone marrow or blood cytogenetic analysis may be performed according to standard hematological practice for patients with prolonged hematological toxicities. Bone marrow analysis should include an aspirate for cellular morphology, cytogenetic analysis and flow cytometry, and a core biopsy for bone marrow cellularity. If it is not possible to conduct cytogenetic analysis or flow cytometry on the bone marrow aspirate, then attempts should be made to carry out the tests on a blood sample. If findings are consistent with MDS/AML, study drug should be discontinued and a full description of findings should be submitted with an SAE report by the investigator to Clovis Oncology for documentation on the Patient Safety database. Presence or absence of blood cytogenetic abnormalities and flow cytometry will be documented on the clinical database.*

#### *5.4.2.1.2 Management of non-hematological toxicity*

Dose interruptions are allowed as required, for a maximum of 2 weeks. Patients who require an interruption in rucaparib for >2 weeks due to toxicity must discontinue study drug. Where toxicity reoccurs following re-challenge with study treatment, then the patient should be considered for dose reduction or must permanently discontinue study treatment.

Study treatment can be dose reduced to 500 mg bid as a first step , to 400 mg bid as a second step and 300mg bid as a third step. Treatment must be interrupted if any NCI-CTCAE grade 3 or 4 adverse event occurs which the investigator considers to be related to administration of study treatment.

Adverse events possibly related to study drug must be resolved to grade 1 or baseline prior to resumption of dosing.

#### **Management of nausea and vomiting**

No routine prophylactic anti-emetic treatment is required at the start of study treatment, however, patients should receive appropriate anti-emetic treatment at the first onset of nausea or vomiting and as required thereafter, in accordance with local treatment practice guidelines.

As per international guidance on anti-emetic use in cancer patients (ESMO, NCCN), generally a single agent antiemetic should be considered eg dopamine receptor antagonist, antihistamines or dexamethasone.

#### **Management of AST/ALT Elevations**

Grade 3 ALT/AST elevations have been successfully treated with treatment interruption and/or a reduction in dose. The data reported as of the data cut-off date suggest that many patients have been able to continue treatment with 600 mg BID following a dose interruption, without any further elevation or recurrence of Grade 3 ALT/AST. The following guidelines have been suggested for managing Grade 3/4 ALT/AST elevations.

Grade 4 ALT/AST elevations: Patients should stop taking rucaparib until values have returned to Grade 2 or better, then resume rucaparib with a dose reduction to 500mg BID. Monitor liver function tests weekly for 3 weeks after rucaparib has been restarted. If a Grade 4 ALT/AST elevation is again observed at 500mg BID, Patients should stop taking rucaparib until values have returned to Grade 2 or better, then resume rucaparib with a dose reduction to 400mg BID. Dose reductions to 300mg BID will be allowed.

Grade 3 ALT/AST elevations, in the absence of other signs of liver dysfunction, should be managed as follows:

- Monitor liver function tests weekly until resolution to  $\leq$  Grade 2.
- Continuation of rucaparib with elevation of ALT/AST up to Grade 3 is permitted provided bilirubin is  $<$  ULN and alkaline phosphatase is  $< 3 \times$  ULN.
- If patient has Grade 3 ALT/AST and continues on rucaparib, and levels do not decline within 2 weeks or they continue to rise, treatment interruption and resolution to  $\leq$  Grade 2 will be required before rucaparib can be resumed, either at the at a reduced dose (500mg BID (if currently taking 600mg BID), 400mg BID (if currently taking 500mg BID), 300mg BID (if currently taking 400mg BID).

### **Interruptions for intercurrent non-toxicity related events**

Study treatment dose interruption for conditions other than toxicity resolution should be kept as short as possible. If a patient cannot restart study treatment within 4 weeks for resolution of intercurrent conditions not related to disease progression or toxicity, the case should be discussed with Principle Investigator.

All dose reductions and interruptions (including any missed doses), and the reasons for the reductions/interruptions are to be recorded in the eCRF.

Study treatment should be stopped at least 3 days prior to a planned surgery. After surgery study treatment can be restarted when the wound has healed. No stoppage of study treatment is required for any needle biopsy procedure.

#### **5.5 End of Treatment/Treatment Discontinuation Visit 28 days after last dose +/- 3 days)**

- Conduct physical exam (including vital signs, height/weight)
- perform laboratory tests: Complete blood count w/Diff, PSA, Comprehensive metabolic panel
- ctDNA blood collection (10ml)
- assess performance status (ECOG). (Appendix A)
- review concurrent medications
- assess AEs
- if patient is discontinuing participation in study, perform radiographic tests: CT A/P and NM Bone Scan (if these have not been performed in the prior 3 months)

#### **5.6 Follow-up (At least every 28 days while active AEs)**

Patients will be followed every 28 days beyond the end of treatment visit if they have withdrawn from study because of AEs. Patients withdrawn from the study because of AEs will be followed until the adverse event has either resolved or stabilized. Reasons for premature withdrawal should be determined and noted. To be performed at each visit will be:

- conduct physical exam (including vital signs, height/weight)

- perform laboratory tests (CBC w/diff, Comprehensive metabolic panel) only as indicated by AEs requiring follow-up
- assess performance status (ECOG). (Appendix A)
- review concurrent medications
- reassess AEs.
- When patient will discontinuing participation in study, perform radiographic tests: CT A/P and NM Bone Scan (if these have not been performed in the prior 3 months)

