## 5. TREATMENT/INTERVENTION PLAN

The following assessments and procedures will occur during the study. A schedule of assessments is provided in Table 1.

	Pre-study	Study Period				Off Treatment / Follow-up
		On Treatment Assessments (Every 28 days) 				
	Day -7 a, h ( $\pm 7$ days)	C1D1 h ( $\pm 3$ d)	C2D1 h ( $\pm 3$ d)	C3D1 h ( $\pm 3$ d)	CnD1 h ( $\pm 3$ d)	
Informed consent	X					
Demographics	X					
Medical history	X					
EKG	X					
Focused Medical history		X	X	X	X	X
Physical exam	X	X	X	X	X	X
Vital signs (P, BP, RR, T)	X	X	X	X	X	X
Height	X					
Weight	X	X	X	X	X	X
Performance status	X		X	X	X	X
Toxicity assessment	X		X	X	X	X
Concomitant meds	X	X	X	X	X	X
Metastatic tumor biopsy	X e				(X) e	
ctDNA (10ml)		X g				X g
Radiologic tests b	X				X b	X b
Laboratory tests c	X	X f	X	X	X	X
Rucaparib		X	X	X	X	
Adverse events			X	X	X	X

Table 1 Study Calendar

Abbreviations: CBC, complete blood count; CT, computerized tomography; MRI, magnetic resonance imaging; PSA, prostate-specific antigen

a Informed consent and radiologic assessments should be obtained within 8 weeks of study start date. EKG should be obtained within 28 days of study start date.

b Radiographic evaluations (CT A/P and NM Bone Scan) every 3 months (if metastatic disease) or every 6 months (for BCR) while enrolled in the study). They are needed within 8 weeks of screening; if previously performed then they are to be performed at screening. CT A/P and NM Bone Scan are to be performed at off-treatment visit if they have not been performed in the prior month.

c CBC w/diff, Complete Metabolic Panel, PSA, lipid panel at each visit. Testosterone, PT/INR, PTT, and Urinalysis at screening visit only and should be obtained within 28 days of study start date.

d Subjects will be followed after completion of rucaparib therapy monthly until toxicities resolve to grade 0-1. No post treatment follow up visit needed otherwise.

e Only for patients with metastatic disease: MANDATORY soft tissue Core tumor biopsy performed pretreatment (Day -7 +/- 7 days), bone biopsies are optional at pretreatment. OPTIONAL soft tissue and bone tumor biopsy on C4D1 (+/- 7 days)

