#### Administration of other anti-cancer agents

Patients must not receive any other concurrent anti-cancer therapy, including investigational agents, while on study treatment.

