#### Subsequent therapies for cancer

Details of first and subsequent therapies for cancer and/or details of surgery for the treatment of the cancer, after discontinuation of treatment, will be collected. Reasons for starting subsequent anti-cancer therapies including access to other PARP inhibitors or investigational drugs will be collected and included in the exploratory assessments of survival.

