## 10.1 Study Endpoints

### 10.1.1 Analysis of the primary endpoint

The primary endpoint of this study is PSA50 response, defined as a decrease in the PSA to 50% less than the baseline PSA upon enrollment in the trial. The decrease must be confirmed by a second measurement at least 4 weeks apart. For purposes of meeting the primary endpoint, patients will be considered to have done so if they have a PSA50 response only while on therapy with rucaparib. PSA values will be measured each cycle during the trial. All patients who are administered at least one dose of rucaparib will be considered evaluable for the primary endpoint. If patients do not have follow-up PSAs after initiation rucaparib therapy due to stopping therapy for toxicity or withdrawing consent, for example, then they will be replaced.

We will estimate the PSA50 response rate, along with the exact 95% confidence interval, for the population of patients.

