#### *10.1.2.3. Radiographic progression-free survival (rPFS)*

Progression-free survival will be measured from the time of first dose to objective tumor progression as defined by RECIST 1.1 for progressive disease or death and summarized using a Kaplan-Meier curve. Progression will be assigned to the earliest observed time. Patients whose disease has not progressed at follow-up will be censored at the date when the last tumor assessment determined a lack of progression.

We will use the Kaplan-Meier method to estimate the median PFS.

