#### *10.1.2.4 Objective response rate*

The objective response rate is defined as the percentage of patients with measurable disease who achieve an objective response by RECIST1.1 criteria (i.e. Complete response or Partial Response) to rucaparib.

We will estimate the objective response rate, along with the exact 95% confidence interval, for the population of patients.

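### Radiographic PFS, and to a lesser degree ORR, have no cut at the start of new anti-cancer therapy, although scans are ordered after rucaparib stops and ADT is no longer barred by then

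*Combined protocol and SAP*

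**What the plan says.** **Scans after the last dose.** Three places order them:

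- Section 5.5 (visit about 28 days after the last dose) has a look-back of 3 months: "if patient is discontinuing participation in study, perform radiographic tests: CT A/P and NM Bone Scan (if these have not been performed in the prior".
- Section 5.6 (follow-up every 28 days, only for men withdrawn because of adverse events): "When patient will discontinuing participation in study, perform radiographic tests: CT A/P and NM Bone Scan", with the same 3-month condition.
- Table 1, footnote b: "CT A/P and NM Bone Scan are to be performed at off-treatment visit if they have not been performed in the prior month".

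**Other therapy.** Section 5.8 states: "Patients must not receive any other concurrent anti-cancer therapy, including investigational agents, while on study treatment". Section 5.8.1 likewise bars hormonal agents during study treatment and in the 6 months before enrollment, not afterwards. Details of later therapies "will be collected and included in the exploratory assessments of survival". No survival assessment appears in the objectives (2.2, 2.3) or in Section 10.

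**Endpoints.**

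- rPFS (10.1.2.3, with matching text in the synopsis) runs from first dose: "Patients whose disease has not progressed at follow-up will be censored at the date when the last tumor assessment determined a lack of progression".
- ORR (10.1.2.4 and synopsis) is the percentage of men with measurable disease "who achieve an objective response by RECIST1.1 criteria (i.e. Complete response or Partial Response) to rucaparib". No time window is given.
- The primary PSA endpoint (10.1.1) counts a response "only while on therapy with rucaparib". ORR and rPFS carry no such restriction.

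**The concern.** These rules do not fit together. Rucaparib stops, the bar on ADT ends, and a scan may follow. Read literally, that scan can be the last tumor assessment that fixes the rPFS censoring date. If ADT has started, the added progression-free time partly reflects ADT.

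Two groups are exposed. The first is men who stop for an adverse event. The second is men who stop on a PSA criterion (PSA progression in the synopsis, confirmed PSA doubling in 6.4). PSA progression is not an rPFS event in 8.1.2.3 or 10.1.2.3, so these men are still at risk for rPFS when they leave treatment.

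ORR and median rPFS are the plan's tumor-based descriptions of rucaparib activity. A single-arm trial has no control group in which the ADT contribution would show. If the rule stays unwritten, someone must decide whether to use these scans after the data are known.

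**Working it through.** **1. The plan's own figures.** The documents give no planning figure for ORR or rPFS. Their design figures concern PSA50: stop if 6 or fewer of 12 respond, ineffective if 17 or fewer of 28. Exact binomial calculation gives early stopping P(X ≤ 6 | 12, 0.5) = 0.613 (stated 0.61), power 0.902 at 75% (stated 90%), and attained one-sided alpha 0.081 (limit 0.1). They are reproduced, and none depends on this point.

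**2. How often the scan conditions are met.** Scans run every 3 cycles (12 weeks) in metastatic disease and every 6 cycles (24 weeks) in BCR. Assume that the last dose falls uniformly between scans and that 3 months is 13 weeks. At the visit 4 weeks after the last dose, the 3-month condition is met if the last scan was more than 13 − 4 = 9 weeks before the last dose:

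- metastatic: (12 − 9)/12 = 25%
- BCR: (24 − 9)/24 = 62.5%

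Under Table 1's 1-month condition, nearly every man is scanned at that visit. The choice between the conditions thus decides whether the last scan tends to fall about a month after stopping or can fall later.

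**3. Effect on median rPFS (assumed inputs).** Exponential progression with median 9 months: λ = ln 2/9 = 0.0770 per month. Toxicity stopping is a competing hazard μ = λf/(1 − f), with f = 15%, 25% and 40% of exits, so μ = 0.0136, 0.0257 and 0.0513. The hazard on ADT is 0.1λ = 0.0077. Over 4 months the chance of staying progression-free is exp(−0.0077 × 4) = 0.97 on ADT, against exp(−0.0770 × 4) = 0.73 without it. A post-stop scan on ADT will therefore nearly always be progression-free and extend the censoring time.

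The simulation used 30 men, 3-monthly scans and Kaplan-Meier medians. It compared censoring at the last scan before stopping with censoring at the post-stop scan on ADT. Rise in the mean Kaplan-Meier median, in months, over f = 15-40%:

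| Last scan after stopping | All such men start ADT | 30% start ADT |
|---|---|---|
| 1 month | 0.1-0.3 | under 0.2 |
| 2-6 months | 0.4-1.9 | 0.1-0.6 |

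A repeat run gave 0.1-0.4 and 0.4-1.8 at full uptake, and 0.0-0.1 and 0.1-0.4 at 30% uptake. The gaps reflect simulation noise and how men who do not start ADT are handled. With the 1-month scan and full uptake, the median was unchanged in 87-96% of simulated trials.

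A separate set of assumptions (true median 12 months, 30 men, 10-30% withdrawn at 3-9 months, censoring extended by 3 or 6 months, medians capped at 36 months) moved the mean median from 13.89 to 14.20 at the low end and from 13.97 to 15.91 at the high end: +0.3 to +1.9 months.

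For scale, a 9-month median with 20 events has an approximate 95% interval of 9 × exp(±1.96/√20), or about 5.8 to 14 months.

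**4. Effect on ORR (assumed inputs).** The number of men with measurable disease is not given. From an assumed 40% rate, one added response moves 4/10 to 5/10 (+10 points), 6/15 to 7/15 (+6.7) or 8/20 to 9/20 (+5). With 15 men the exact 95% interval moves from 16-68% to 21-73%.

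**The case against.** **That these scans count is inferred.** A reader might infer that the plan declares post-treatment scans countable and so credits ADT effect to rucaparib. No sentence says so. What stands is narrower: a rule that names the last tumor assessment includes such scans unless a further rule is added.

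**The scans are conditional.** Sections 5.5 and 5.6 require one only if none was done in 3 months. Under Table 1 most men would be scanned about 4 weeks after the last dose, and a 5.6 scan would not be due for 3 months after that. On that reading the effect is mostly the small, 1-month one. This is a fair limit, but the conditions conflict, so the later scan cannot be ruled out.

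**ORR is partly protected.** A reader might infer an ORR inflated by 5 to 10 points. Section 10.1.2.4 speaks of response to rucaparib, and 8.3.1 asks that a favorable change be confirmed on a second scan. A response first seen on an exit scan would normally have no later protocol scan. This largely stands, although Section 10 neither repeats the confirmation requirement nor defines a cut-off.

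**ADT may not have started.** The rationale describes ADT as an option upon progression. If that progression is radiographic or clinical, the rPFS event has already occurred. Men were also enrolled because they declined or were ineligible for ADT. Uptake after a toxicity stop is therefore unknown, hence the 30% column. Without ADT, a late off-drug scan can equally record progression.

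**A treatment-policy rPFS is legitimate.** True, if it is chosen and stated. The plan states no choice.

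**Conclusion.** The gap is real but modest. It is clearest for rPFS, whose written censoring rule would include a progression-free scan taken on ADT, both in men who stop for an adverse event and in men who stop for PSA progression. For ORR it is a lesser ambiguity.

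Under the assumptions above, the rise in the mean Kaplan-Meier median runs from about 0.1 month (scan at 1 month) to about 1.9 months (scan at 2-6 months, 40% stopping, all on ADT). At 30% uptake it is under 0.2 and about 0.1-0.6 months. The documents supply none of the true median, toxicity-stop rate, ADT uptake or ADT effect, so these are illustrations and not forecasts. A reader might take the upper figure as the expected bias. The documents do not support that, because it needs late scans and universal ADT together.

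PSA50, sample size, stopping rule and power are unaffected. The change is worth making because these estimates have no control arm behind them and the remedy is short.

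**What to change.** - In 10.1.2.3 and the synopsis: use only tumor assessments before the first new anti-cancer therapy, and censor a man without progression at his last such assessment.
- Add one rPFS sensitivity analysis that counts the start of new therapy as an event. Censoring at new therapy may be informative, most plainly in men who switch because PSA is rising.
- In 10.1.2.4 and the synopsis: count only CR or PR seen before the first new anti-cancer therapy.
- In 5.8, under subsequent therapies: state that the start date of the first subsequent therapy is recorded and used in these analyses. The present text mentions details and reasons but not expressly a date, and ties them to a survival assessment that the plan does not otherwise contain.
- Reconcile the 1-month condition in Table 1 footnote b with the 3-month condition in 5.5 and 5.6.

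The cost is a few sentences and, at most, one added date field. ORR and rPFS may look slightly less favorable. No change to sample size or to the primary analysis is needed.

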## 5.7 Correlative/Special Studies

### 5.8.1. DNA sequencing

FFPE biopsy tissue will be sent to Foundation Medicine for next generation sequencing, based upon their commercially available platform.

### 5.8.2. mRNA expression profiling

A sample of FFPE biopsy tissue will be sent to GenomeDx for RNA expression profiling.

### 5.8.3. PARP-1, PARP-2, γH2AX, RAD51, 53BP1 mRNA/ Protein Analysis

A sample of biopsy will be sent to the [name] laboratory for analysis.

## 5.8 Concomitant Medications

Because of the potential for drug-drug interaction, the concurrent use of all other drugs, over-the-counter medications, or alternative therapies must be documented on the case report form (CRF).

### Hematopoietic Growth Factors and Blood Products

Erythropoietin, darbepoetin alfa, and/or hematopoietic colony-stimulating factors for treatment of cytopenias should be administered according to institutional guidelines. Transfusion thresholds for blood product support will be in accordance with institutional guidelines.

### CYP450 Isoenzyme Inhibitors, Inducers, and Substrates

Based on results of in vitro CYP interaction studies, caution should be used for concomitant medications with narrow therapeutic windows that are substrates of CYP2C19, CYP2C9, and/or CYP3A. Selection of an alternative concomitant medication is recommended.

### Examples of CYP Substrates with Narrow Therapeutic Range

CYP Enzyme	Substrates with Narrow Therapeutic Range a
CYP2C9	Warfarin, phenytoin
CYP2C19	S-mephenytoin

CYP3A	Alfentanil, astemizole, cisapride, cyclosporine, dihydroergotamine, ergotamine, fentanyl, pimozide, quinidine, sirolimus, tacrolimus, terfenadine
-------	---

The table is based on the Draft FDA Guidance on Drug Interaction Studies — Study Design, Data Analysis, Implications for Dosing, and Labeling Recommendations, 2012.

a CYP substrates with narrow therapeutic range refers to drugs whose exposure-response relationship indicates that small increases in their exposure levels by the concomitant use of CYP inhibitors may lead to serious safety concerns (eg, Torsades de Pointes).

#### Anticoagulants

Caution should be exercised in patients receiving rucaparib and concomitant warfarin (Coumadin) as rucaparib showed a mixed inhibition of CYP2C9 *in vitro*. If appropriate, low molecular weight heparin should be considered as an alternative treatment. Patients taking warfarin should have international normalized ratio (INR) monitored regularly per standard clinical practice.

#### Anti-emetics/Anti-diarrheals

If a patient develops nausea, vomiting and / or diarrhea, then these symptoms should be reported as AEs and appropriate treatment of the event given.

#### Administration of other anti-cancer agents

Patients must not receive any other concurrent anti-cancer therapy, including investigational agents, while on study treatment.

#### Subsequent therapies for cancer

Details of first and subsequent therapies for cancer and/or details of surgery for the treatment of the cancer, after discontinuation of treatment, will be collected. Reasons for starting subsequent anti-cancer therapies including access to other PARP inhibitors or investigational drugs will be collected and included in the exploratory assessments of survival.

##### *5.8.1 Prohibited before enrollment and during administration of study treatment*

Medications that are prohibited during study treatment and in the prior 6 months prior to enrollments: LHRH agonist / antagonist therapy, androgen receptor antagonists, and androgen synthesis inhibitors. 5-alpha reductase inhibitors are allowed if subject has been taking stable dose of medication for prior 6 months.

